where i indexes the site ($i = 1, 2, 3, 4, 5, 6$); j the implementation phase (1: baseline period; 2: active implementation phase; 3: one year after the active implementation phase); k the encounter at the i^{th} site and the j^{th} phase ($k = 1, 2, \dots, n_{ij}$); n_{ij} is the total number of encounters at the i^{th} site and the j^{th} phase; $X_{ij,k}$ and $Z_{ij,k}$ the indicators of the active implementation phase and one year after the active implementation phase, respectively; $W_{ij,k}$ the vector of the k^{th} encounter's characteristics at the i^{th} site and the j^{th} phase that could include the site characteristics; $Y_{ij,k} = 1$ the indicator of observation of “Without-Fail” care process on the k^{th} encounter at the i^{th} site and the j^{th} phase. For this model, μ represents the average log odds of Without-Fail care across the 6 sites at baseline; θ the log odds ratio between the active implementation phase and the baseline indicating the intervention effect during the active implementation phase; and γ the log odds ratio between one year after the active implementation phase and the baseline indicating the intervention sustainability effect post the implementation; α_i and β_j are the site and phase specific random effects that are assumed to be multivariate normal. After fitting the model, the normal theory can be applied to test the intervention effect at the active implementation phase and the intervention sustainability effect.

Secondary Aim 2 Analyses: Several secondary effectiveness analyses are planned.

Comparison to Matched Controls

Six control sites will be matched to each of the six PREVENT active implementation sites on the basis of: TIA patient volume, facility complexity (i.e., teaching status, intensive care unit level), and quality of care (measured by the without-fail rate). The total number of control sites will be 36. The definition of the baseline period (the specific start and end dates of the one-year baseline period) for each matched control site will be identical to the definition used for the PREVENT active site to which the controls are matched. We will compare changes in quality and outcomes at control sites to changes at PREVENT sites as a method for assessing temporal trends.

Changes in Individual Processes of Care

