An examination of the care rate of facility process for each of the seven primary processes of care across the six sites from the baseline period to post-implementation period will be conducted using the same analytical template as outlined for the primary analysis. A single risk adjustment model will be developed for use in evaluating the seven processes of care and will focus on baseline patient characteristics as follows:

Process	Risk Adjustment Variable
Anticoagulation for atrial fibrillation	Past history of atrial fibrillation (versus new afib)

	Use of anticoagulation prior to index event PMH of GI or intracranial hemorrhage Age Dementia
Antithrombotics	PMH of CAD, MI PMH of diabetes Anti-platelet or anticoagulant prior to index
Brain imaging	PMH of stroke or TIA
Carotid artery imaging	PMH CEA or stent PMH of PVD
High or moderate potency statin	Use of statin prior to index event PMH of CAD, MI PMH of diabetes History of intracranial hemorrhage LDL-cholesterol Age
Hypertension control	Kidney disease, dialysis PMH diabetes PMH of CAD, MI Antihypertensive meds before index event BP before the event and at discharge Homeless PCP visit
Neurology consult	Neurology FTE
General	Hospice, comfort care, AMA Admitted versus ED Transferred into or out of our facility Nights/weekends presentation

90-Day Recurrent Stroke Rate

(1) The 90-Day recurrent stroke rate will be estimated at each site before (baseline and pre-implementation phase) and after (active implementation phase and one year after the active implementation phase) the intervention to examine the temporal trends in intervention effectiveness for reducing the 90-day recurrent stroke rate. The 95% confidence intervals for the rates will be provided.

(2) The similar GLMM at patient level as described for the primary analysis will be developed for the incidence of 90-day recurrent stroke across the six sites and the whole study period to study the mean change of this rate. For this model, the indicator of Without Fail care at the encounter level will be incorporated into the model as the main exploratory variable to examine if the improvement of the Without Fail care rate will result in significant reduction of the 90-Day recurrent stroke rate.

90-Day Mortality

The analysis plan for the 90-day recurrent stroke rate (described above) will also be implemented for the 90-Day Mortality.

Disease-free Survival Analysis

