4.5 Risk Score

As part of the PREVENT program, participating sites are provided with their patient risk score which is a measure of the risk of 1-year mortality. We are interested in two analyses related to the risk score.

1. How did the sites use the patient risk score? This assessment will be based on qualitative interviews with sites at 6-months and 1-year post-implementation.
2. Risk score validation. For this analysis, all VAMCs will be included (not only PREVENT sites). Predicted risk scores, with their 95% confidence intervals, will be compared with observed 1-year mortality and its 95% confidence interval.

TABLE SHELLS

Table 1. Baseline Characteristics: at the Facility-Level

	Baseline (Control)	Pre- Implementation	Post- Implementation (Active Implementation)	Sustainability
Patient Characteristics				
Facility Characteristics				
90-Day Mortality Rate				
90-Day Recurrent Stroke Rate				
90-Day Recurrent TIA Rate				
90-Day Recurrent Stroke or TIA Rate				

Table 2. Unadjusted Effectiveness: at the Facility-Level

THIS IS THE PRIMARY ANALYSIS in terms of the data periods being compared.

	Baseline (Control)	Post- Implementation (Active Implementation)	P- VALUE
Individual Processes of Care			
Anticoagulation for Atrial Fibrillation			
Antithrombotics			
Brain Imaging			
Carotid Artery Imaging			
High/Moderate Potency Statin			
Hypertension Control			
Neurology Consultation			
Mean Facility Consolidated Measure Rate			
Mean Facility Without-Fail Rate			

Table 3. Hierarchical Model: Includes adjustment for patient and facility characteristics

The same approach described for the modelling the without-fail rate can be used to model the outcome rates.

Table 4. Temporal Trends in Quality of Care: Unadjusted

	Baseline (Control)	Pre- Implementation	Post- Implementation (Active Implementation)	Sustainability
Individual Processes of Care				
Anticoagulation for Atrial Fibrillation				
Antithrombotics				
Brain Imaging				
Carotid Artery Imaging				
High/Moderate Potency Statin				
Hypertension Control				
Neurology Consultation				
Mean Facility Consolidated Measure Rate				
Mean Facility Without-Fail Rate				

REFERENCES

1. Williams L. *Stroke Quality Enhancement Research Initiative (QUERI) Strategic Plan and Renewal Report*. 2013.

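### The risk-adjustment list for the seven process models is labelled baseline but includes discharge BP, admission status and transfer out, which are settled after care starts and can distort the adjusted process effects

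*Combined protocol and SAP*

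**What the plan says.** In section 4.2, under Changes in Individual Processes of Care, the plan states that "A single risk adjustment model will be developed for use in evaluating the seven processes of care" and that this model "will focus on baseline patient characteristics as follows". The table that follows gives the variables by process:

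- The hypertension-control row includes "BP before the event and at discharge".
- The General row, attached to no single process, includes "Hospice, comfort care, AMA Admitted versus ED Transferred into or out of our facility".

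The process analyses are to be run "using the same analytical template as outlined for the primary analysis". That template is the patient-level GLMM in Primary Aim 2 Analysis. Its coefficient θ is defined as "the log odds ratio between the active implementation phase and the baseline indicating the intervention effect during the active implementation phase", and the covariate vector W enters the same linear predictor.

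Among the table shells, Table 2 compares each of the seven processes between baseline and post-implementation without adjustment, with p-values. Table 4 gives unadjusted rates by period. Table 3 is the hierarchical model, described as one that "Includes adjustment for patient and facility characteristics". The planned sensitivity analyses vary which TIA events are counted. None varies the covariate list.

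**The concern.** The label and the list disagree. A patient's BP before the event is a baseline value; BP at discharge is not. Whether a patient is admitted or sent home from the ED, and whether the patient is transferred out, are also decided after arrival.

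This matters because of how the coefficient is read. If the program changes a covariate and that covariate affects the outcome, the adjusted phase coefficient no longer carries the part of the effect that runs through it.

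For discharge BP the documents supply a plausible route. Hypertension control is one of the seven processes. The Background names antihypertensive intensification as a care gap, delivered to 27% of eligible Veterans. The program includes pharmacist-based medication management, protocols and templates. Discharge BP therefore sits between the care being improved and the outcome being modelled.

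For admission and transfer out the route is only possible: imaging and neurology consultation may depend on where the patient is cared for. Because a single model serves all seven processes, these variables may enter every adjusted process analysis.

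**Working it through.** No figure in the plan depends on this covariate list, so there is none to reproduce. The check has two parts.

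**1. When each listed variable is settled**

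| Variable | Settled | Route from the program in the documents |
|---|---|---|
| BP before the event | before arrival | none |
| BP at discharge | after care starts | yes: BP treatment is a target |
| Admitted versus ED | after arrival | not stated |
| Transferred in | at or before arrival | none |
| Transferred out | after arrival | not stated |

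**2. What adjustment does, under assumed inputs**

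Every input below is an assumption. The documents give no program effect on discharge BP, admission or transfer.

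*Discharge BP* (simulation, 400,000 encounters; A = 1 post-implementation, 0 baseline; d = program effect on discharge BP in mmHg):

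- pre-event BP ~ N(150, SD 12)
- discharge BP = 145 + 0.5 × (pre-event BP − 150) − d × A + N(0, SD 10)
- later BP = 142 + 0.6 × (discharge BP − 145) − (6 − 0.6d) × A + N(0, SD 10)
- control = later BP below 140

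The total effect on later BP is fixed at 6 mmHg, of which 0.6d runs through discharge BP. The expected share removed is therefore 0.6d/6 = 0.1d. Control rises from about 43.5% to 62.8%. Standardised risk differences (RD) from the logistic models:

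| d (mmHg) | RD, pre-event BP only | RD, adding discharge BP | Share removed |
|---|---|---|---|
| 0 | 0.191 | 0.191 | 0% |
| 2 | 0.194 | 0.154 | (0.194 − 0.154)/0.194 = 21% |
| 4 | 0.192 | 0.116 | (0.192 − 0.116)/0.192 = 40% |
| 6 | 0.193 | 0.077 | (0.193 − 0.077)/0.193 = 60% |
| 8 | 0.194 | 0.038 | (0.194 − 0.038)/0.194 = 80% |

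The shares match 0.1d. Risk differences are used because the odds ratio is not collapsible: at d = 0, adding discharge BP raises the log odds ratio from 0.824 to 0.991 although nothing is mediated. At d = 2 it falls only from 0.835 to 0.797. A comparison of log odds ratios alone would therefore mask part of the loss.

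*Admitted versus ED* (arithmetic). Assume baseline pass rates of 0.75 if admitted and 0.35 if ED, 60% admitted at baseline, and a direct program effect of 0.5 on the log odds.

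- Baseline rate = 0.60 × 0.75 + 0.40 × 0.35 = 0.590.
- Post-implementation pass rates: 3 × e^0.5 / (1 + 3 × e^0.5) = 0.832 if admitted; (0.35/0.65) × e^0.5 / (1 + (0.35/0.65) × e^0.5) = 0.470 if ED.
- Total RD = a × 0.832 + (1 − a) × 0.470 − 0.590, where a is the post-implementation admitted share.
- Adjusted RD = m × (0.832 − 0.75) + (1 − m) × (0.470 − 0.35), where m = (0.60 + a)/2.

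| a | Total RD | Adjusted RD | Adjusted relative to total |
|---|---|---|---|
| 0.50 | 0.061 | 0.099 | larger |
| 0.60 | 0.097 | 0.097 | equal |
| 0.70 | 0.133 | 0.095 | smaller by about 29% |
| 0.80 | 0.170 | 0.093 | smaller by about 45% |

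A simulation of the same set-up gave 0.061 and 0.101, 0.098 and 0.097, 0.132 and 0.095, and 0.167 and 0.090, which agrees to within sampling error. The sign of the distortion follows the direction in which admission moves, and there is none if admission does not move.

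**The case against.** The strongest reply concerns the disposition variables. Sites were not randomised to waves and the comparison is before versus after. Admission and transfer out may reflect severity or the opportunity to deliver care, and either could shift between periods for reasons unrelated to the program. They may be confounders as well as mediators. No part of the documents says that the program changes admission or transfer; neither is a target process or named in the five components. This stands, and it is why both models should be reported.

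A second reply is that Table 2 already gives a comparison of each process free of these covariates. This also stands and limits the reach. It does not settle the matter, because a non-randomised before-after comparison has reason to adjust for case mix, and the planned adjusted model is the one affected.

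A third is that the documents do not say when hypertension control is measured. True. If it is read at or near discharge, the covariate nearly duplicates the outcome; if later, discharge BP is an intermediate step. Neither makes it a baseline value.

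A reader might infer more than the documents support:

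- *That the adjusted results would understate the program.* Not established. Nothing is lost if discharge BP does not move, and for admission the adjusted effect can exceed the total effect.
- *That leaving against medical advice (AMA) belongs with the other variables.* Nothing in the documents suggests that the program changes it.
- *That the Without-Fail result is affected.* The list is tied to the seven processes. W is left open in the primary model, and the plan does not say whether this list fills it.

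**Conclusion.** The point holds in limited form. The list is labelled baseline but contains three variables settled after care starts. Discharge BP is the clear case: adjusting hypertension control for it can remove part of the effect that the model is meant to estimate. Admitted versus ED and transfer out are weaker cases, with possible distortion in either direction, conditional on the program changing them.

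The size cannot be computed from the documents. The illustrations rest wholly on assumed inputs: 0% to about 80% of the hypertension-control effect removed for a program effect on discharge BP of 0 to 8 mmHg, and an adjusted process effect above, equal to or below the total effect according to how admission moves. Only the adjusted secondary process models are affected as the plan is written.

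**What to change.** In section 4.2, Changes in Individual Processes of Care:

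1. Remove BP at discharge from the main adjustment model. Keep BP before the event.
2. Restrict the main model to values known at or before presentation. Transfer in, prior medication, medical history and nights/weekends presentation stay.
3. Report the process models with and without admitted versus ED and transfer out, the fuller model being a labelled sensitivity analysis. Give standardised risk differences beside the odds ratios, since odds ratios from different covariate sets are not directly comparable.
4. State whether this list supplies W in the Without-Fail model and Table 3. If it does, apply the same restriction there.

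No case is made here for removing AMA. Nor should hospice or comfort care become an eligibility exclusion, because that would change the measure itself. The SAP need only say when these are recorded and which model they enter.

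The cost is SAP wording, a shorter covariate list and one extra set of model runs on data already planned. The small downside is some loss of case-mix adjustment in the main model, which the sensitivity model covers.

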1. BACKGROUND

Approximately 8,500 Veterans with transient ischemic attack (TIA) or stroke are cared for in a Department of Veterans Affairs (VA) Emergency Department (ED) or inpatient ward annually.¹ Patients with transient ischemic attack (TIA) are at very high risk of recurrent vascular events; over the long-term 11% per year will have a stroke, myocardial infarction or vascular death.²⁻⁴ Because patients with TIA and minor stroke have little neurological impairment yet are at high risk of recurrent events, including disabling stroke, they are ideal candidates for interventions to reduce their risk of adverse events. Several studies have demonstrated that interventions which deliver timely care reduce the risk of recurrent vascular events by 70%.⁵

Our group has assessed the quality of care for Veterans with TIA and minor stroke cared nationwide and has found considerable gaps in care quality (e.g., 51% of eligible Veterans receive carotid imaging, 27% receive indicated antihypertensive medication intensification).⁶ In other words, Veterans are not receiving the timely, guideline concordant care they need to prevent recurrent vascular events. The objective of the PREVENT project is to develop and evaluate an intervention program to improve the quality of care for Veterans with TIA and minor stroke.

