4.2 Aim 2 Methods (Effectiveness)

Design

This five-year stepped-wedge^{20,21} evaluation includes a total of 6 sites, where active implementation is initiated in 3 waves each of which includes 2 sites. The project involves three

[figure not shown]
phases at each of the six sites: a one year-baseline phase, a one-year active implementation phase, and a sustainability phase of at least one year in duration follows the end of active implementation.

Power and Sample Size

The six site, stepped wedge design provides >90% power to detect an improvement in the mean facility Without-Fail rate from 25% during the baseline data period to >50% during the active implementation data period. The goal for the sample size was to recruit sites with at least 50 TIA patients per year, however, power was preserved with at least 30 TIA patients per year.

The figures below provide the plots of the power calculated based on the modified formula for testing the intervention effect $H_0: \theta = 0, H_1: \theta = \theta^M$ for the intervention effect size θ^M ranging from 0.1 to 0.3 when taking account for a potential decrement in intervention effect over time γ . The plot was based on a total of 6 clusters with a cluster sample size of 30, 50 and 70, respectively. The results demonstrated that this variant of SWD generally has a reasonable power (greater than or equal to 0.90) for detecting the intervention effect when the effect size is at least 0.15 with a cluster size no less than 30. The coefficient of variation (CV) was set at 0.2, 0.4, 0.6, and 0.8 to cover a wide range of the between-hospital variation. The CV seemed to have little effect on power.

Site Selection

Sites were invited to participate on the basis the basis of demonstrated gaps in quality of care (identified using the validated eQMs). Specifically, sites were invited to participate if they had baseline without-fail rates of <50%. Invitations were sent via email to higher volume sites first and recruitment continued until 6 participating sites were identified. No minimum threshold on volume was employed because our goal was to include sites which were diverse so that the results might be widely generalizable across the full spectrum of VHA facilities.

Allocation of Sites to Waves

Although some stepped-wedge trials randomly assign facilities to waves, PREVENT sites were allocated to waves on the basis of the pragmatics of the ability to schedule baseline and Kick-Off meetings.

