We will examine disease-free survival over the course of 1-year after the index event. We will use Cox proportional hazards modeling, censoring patients for either death or recurrent stroke and examine the relationship between quality of care and disease-free survival.

Temporal Trends in Effectiveness

An examination of the mean Without-Fail rate for the baseline data period through sustainability for all non-participating VA sites with at least 10 TIA patients per year. Given that Indianapolis VAMC has served as the coordinating center, we would not include that site in the analyses.

Consolidated Quality Measure

A consolidated measure of quality defined as the number of passes divided by the number of eligible patients across the seven primary processes of care will be compared for baseline versus post-implementation periods using the same approach described above for the Without-Fail rate analysis.

Secondary Processes of Care

An examination of the secondary processes of care: baseline versus active implementation data periods.

Sensitivity Analyses

The primary analysis will include the first TIA event per patient during the entire study period. In sensitivity analysis, we will include (1) the first event per period and (2) all TIA events in the analysis.

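### The 1-year disease-free survival Cox model names no failure event and lists death and recurrent stroke, its natural endpoint events, as reasons for censoring

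*Combined protocol and SAP*

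**What the plan says.** The only description of this analysis is the short paragraph headed Disease-free Survival Analysis, among the secondary Aim 2 analyses in Section 4.2. It sets a one-year horizon from the index event and then states: "We will use Cox proportional hazards modeling, censoring patients for either death or recurrent stroke". The purpose is to "examine the relationship between quality of care and disease-free survival". The paragraph does not say which occurrence counts as a failure, does not define disease-free, and gives no other reason for censoring.

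Elsewhere the plan treats the same two occurrences as outcomes:

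- Recurrent stroke (Section 4.2, 90-Day Recurrent Stroke Rate): a patient-level mixed model "will be developed for the incidence of 90-day recurrent stroke across the six sites".
- Death (Section 4.2, 90-Day Mortality): "The analysis plan for the 90-day recurrent stroke rate (described above) will also be implemented for the 90-Day Mortality".

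Two further vascular events are mentioned, but neither is tied to the survival analysis. The Table 1 shell has a row for "90-Day Recurrent TIA Rate". The Background describes long-term risk as "over the long-term 11% per year will have a stroke, myocardial infarction or vascular death".

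**The concern.** A Cox model needs two things stated: the event that counts as a failure, and the circumstances in which a patient leaves observation without having failed. Here the first is missing, and the second is filled with the two occurrences that would ordinarily be the failures. An endpoint called disease-free survival ends when the patient dies or the disease recurs, so the written rule gives both occurrences the opposite status to the one the endpoint's name implies.

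This is the only planned analysis that relates quality of care to patient outcomes over a full year. If the rule is followed as written, it does not deliver the quantity it is named for. If it is silently reversed, the make-up of the endpoint is settled by whoever writes the program, possibly after outcomes are visible.

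**Working it through.** The plan states no event count, hazard ratio, alpha or power for this analysis, so there is no figure to reproduce. The check is of the rule itself.

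**Step 1. What the model uses.** Let patient *i* have follow-up time T_i, status d_i (1 = failure, 0 = censored) and quality-of-care covariate x_i. The Cox partial likelihood is

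L(β) = product, over patients with d_i = 1, of exp(βx_i) / Σ_{j at risk at T_i} exp(βx_j).

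Only patients with d_i = 1 contribute a factor. Censored patients appear only in the risk sets.

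**Step 2. Apply the written rule.** Death gives d = 0. Recurrent stroke gives d = 0. A patient who reaches one year free of both also has d = 0. If no other event is intended, every d_i is 0. The product is then empty, so L(β) = 1 and log L(β) = 0 for every β. The likelihood is flat and carries no information about the hazard ratio. A numerical check on simulated data (600 patients, an assumed number) gave a partial log-likelihood of 0.0 at β = −1, 0 and 1.

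**Step 3. Compare the possible readings.** Write h_D, h_S and h_T for the hazards of death, recurrent stroke and recurrent TIA. Survival free of death and stroke has hazard h_D + h_S.

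| Reading | Failure (d = 1) | Censored (d = 0) | What is estimated |
|---|---|---|---|
| As written, no other event | none | death, stroke, end of year | nothing; likelihood flat |
| As written, recurrent TIA supplied as the event | recurrent TIA | death, stroke, end of year | effect on h_T only |
| Only one of death or stroke censored (departs from the text) | the other one | the censored one, end of year | effect on h_S only, or on h_D only |
| Status reversed (departs from the text) | first of death or stroke | end of year or end of data | effect on h_D + h_S |

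In the second row the model can be fitted, but a patient who dies or has a stroke contributes only event-free time up to that point. Neither h_D nor h_S enters as a failure hazard. The result is a cause-specific hazard of TIA with death and stroke as competing events. Only the last row matches the name of the analysis.

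**Step 4. Look for a definition elsewhere.** None is given. The 90-day sections support death and recurrent stroke as outcomes but do not mention disease-free survival. The Table 1 shell lists recurrent TIA at 90 days, without a link to the Cox model. The Background phrase includes myocardial infarction and restricts death to vascular death, but it describes prognosis and does not define an endpoint.

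**Step 5. Look for the real censoring rule.** None is stated. The sustainability data period ends on 9/30/19 at every site. If outcome data also stop then, which the plan does not say, patients with an index event after about 9/30/18 would lack a full year of follow-up and would need administrative censoring.

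**The case against.** The strongest reply is that any analyst will see what was meant. The paragraph is about disease-free survival, it puts death and recurrent stroke together, and the plan has just modelled both as outcomes. A program with no failures would not produce an estimate, so the slip would surface at once. The analysis is one of several secondary ones, has no table shell of its own, and carries no stated power.

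Much of this stands. The likely intent can be recovered, and the practical risk is less a run with zero failures than an endpoint whose make-up is not fixed in advance. But recovery means reversing a stated rule and then deciding, without guidance, whether recurrent TIA or myocardial infarction belongs in the event. The link from the 90-day outcomes to this endpoint is also an inference.

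Three stronger readings are tempting and are not supported:

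- A reader might infer that the analysis must have zero failures. That holds only if no other event is intended, and the plan does not say so.
- A reader might take the Section 4.2 sensitivity analysis that admits all TIA events as evidence that recurrent TIA is the failure event. That sentence concerns which index events enter the analysis. It does not define an outcome.
- A reader might try to count the events miscoded by combining the Background rate of 11% per year with the planning volumes of 30 or 50 patients per site-year. The documents do not support such a count. The 11% belongs to a different endpoint, Section 4.2 says no minimum volume was applied, and the paragraph does not say which periods enter the model. The sustainability windows are also unequal; site F's runs only from 5/13/19 to 9/30/19.

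**Conclusion.** The point holds as a defect in a stated rule, not merely as missing detail. As written, the Cox analysis either has no failures or estimates the cause-specific hazard of an event the plan does not name. Neither is disease-free survival. This conclusion rests on the text and on the form of the partial likelihood, and needs no assumed event rate. That death and recurrent stroke were meant as a composite failure is an inference from the endpoint's name and the 90-day analyses. It is the likely reading, but the documents do not confirm it.

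The documents give no figure for the size of the effect on this analysis, so none is offered. The reach is limited to this one secondary analysis. A reader might infer that the outcome analyses in general are compromised, but the primary Without-Fail comparison and the 90-day stroke and mortality models do not use this rule and are unaffected.

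**What to change.** Replace the censoring clause with a definition along these lines:

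*Event = first of death from any cause or recurrent stroke within 365 days of the index event; event-free patients are censored at day 365 or at the end of available data, whichever is earlier.*

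Because the intent is inferred, the sponsor should confirm this reading before the analysis is run and state whether recurrent TIA or myocardial infarction also counts as an event. If the sponsor did mean a different single event with death and stroke censored, the plan should name that event, call the result a cause-specific hazard rather than disease-free survival, and say how competing events are handled.

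The cost is one sentence in the analysis plan and one decision by the sponsor. The proposed death-or-stroke definition needs no new data.
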